### **7.8.3. Clinical Laboratory**

Hematology and chemistry results will be summarized by treatment regimen and overall using descriptive statistics for observed and change from baseline to Last.

The PCI laboratory values will be summarized by treatment regimen and overall using frequency counts and percentages. Refer to [Table 16](#) for PCI criteria.

A subject listing (including urinalysis results) will be presented for all laboratory parameters. Serum and urine pregnancy test results will also be listed.

### **7.8.4. Body Height, Body Weight and BMI**

Body height, weight and BMI at Screening will be summarized by treatment regimen and overall and listed as baseline characteristics as mentioned in Section [7.3](#).

Body weight will be summarized by treatment regimen and overall using descriptive statistics for observed and change from baseline values for all visits.

#### **7.8.5. Vital Signs**

Vital signs (systolic and diastolic blood pressure, pulse rate, respiratory rate, and body temperature) will be summarized by treatment regimen and overall using descriptive statistics for observed and change from baseline values for all assessments visits. Baseline (study baseline) will be the vital sign value taken at Day 1 predose for the by-visit analyses.

Vital signs will additionally be summarized by treatment regimen and overall for observed and change from baseline values for all time points on each injection day. For each injection day, baseline (injection day baseline) will be a predose value taken on that day.

The PCI vital signs values will be summarized by treatment regimen and overall using frequency counts and percentages. Refer to [Table 17](#) for PCI criteria.

A subject listing will be presented for vital sign results.

#### **7.8.6. 12-Lead ECG**

The investigator interpretation of ECG results (normal, abnormal not clinically significant or abnormal clinically significant) will be summarized by treatment regimen and overall using frequency counts and percentages.

A subject listing will be presented for the investigator interpretation with other details.

#### **7.8.7. Physical Examination**

Physical examination results (by body system) at baseline and Last will be presented by treatment regimen and overall using frequency counts and percentages.

A subject listing will be presented for the physical examination result (by body system).

#### **7.8.8. Immunogenicity**

The immunogenicity analysis of binding and neutralizing anti-AUX-I and anti-AUX-II antibodies will summarize the number of subjects with an immunogenicity sample, the percentage of subjects with a positive sample, and the average titer level of the positive samples at Day 1 and Last by total number of treatment sessions received. The titer levels will be logarithmically transformed prior to being summarized.

Neutralizing antibody results will be summarized by total number of treatment sessions as percentage of positive/negative.

A listing of immunogenicity results by subject will be provided.

**Note:** For immunogenicity table “x treatment sessions” presents a cohort of subjects who received a total of x treatment sessions during the study.

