### 8.9. Biomarkers

#### 8.9.1. Immunogenicity Assessments

Anti-AUX-I and anti-AUX-II antibodies and anti-AUX-I and anti-AUX-II neutralizing antibodies will be evaluated in samples (4-mL tubes of blood) collected from all subjects at times outlined in the Schedule of Activities. These samples will be tested by the sponsor or sponsor's designee. The titer of confirmed positive samples will be reported. Other analyses may be performed to verify the stability of antibodies and/or further characterize the immunogenicity of study treatment.

The serum samples obtained will be processed, stored and then shipped frozen on dry ice to Endo's appointed laboratory for the determination of anti-AUX-I and anti-AUX-II antibodies. Specific instructions for the collection, processing, storage, handling and shipment of the immunogenicity samples will be provided in a separate document.

De-identified immunogenicity samples may be stored for a maximum of 2 years (or according to local regulations) following the last subject's last visit for the study at a facility selected by the sponsor to enable further analysis of immune responses to study treatment develop methods, assays, prognostics and/or companion diagnostics related to specify the intervention target, disease process, pathways associated with disease state, and/or mechanism of action of the study treatment.

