#### 9.3.3. Other Analyses

The incidence of subjects meeting specific potentially clinically important (PCIs) criteria for both vital signs and clinical safety laboratory results will be summarized.

Anti-AUX-I and anti-AUX-II antibody levels and neutralizing antibody levels will be summarized using descriptive statistics for the actual value at the visit.

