### **6.3. Handling of Missing Data**

Subjects who withdraw from the study after the initiation of the study drug will not be replaced and available data for these subjects until the point of withdrawal will be summarized.

The missing baseline assessment will not be imputed.

For categorical variables with missing values, a category documenting the frequency of missing values will be displayed in the summary tables.

For Body Q- Appraisal of Cellulite, if missing data at a visit is less than 50% of the scale's items, the mean of the completed items multiplied by 11 will be used to determine total score. Also, if the missing data at a visit is more than 50% then for that subject raw sum score will be considered as missing.

There will be no imputation of missing values for safety data, however missing relationship between AE and study drug will be considered as related to study drug following worst case principle. Missing severity of an AE will be summarized as a severe AE. Duration of the AE is classified in the '>21 Days' category if an AE is ongoing for more than 21 days by the last visit of the subject in the study.

Immunogenicity samples with a positive titer value will undergo a log transformation for analyses. Samples with titer level less than 10 will be assigned or imputed as a log transformed titer of 1 for analyses.

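### Antibody titer is averaged over positive samples only, separately at Day 1 and Last, so the two means can cover different subjects and no within-subject response is summarised

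*SAP*

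**What the plan says.** The immunogenicity objective is secondary, and its endpoints are anti-AUX-I and anti-AUX-II antibody levels and neutralizing antibodies (SAP Table 1). SAP 3.18 schedules one sample on Day 1 before treatment and one at Day 180 or early termination, so most subjects should have a pair.

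For the analysis, SAP 7.8.8 reports how many subjects were sampled and what share of them were positive. Antibody level is then given as "the average titer level of the positive samples at Day 1 and Last by total number of treatment sessions received". It adds: "The titer levels will be logarithmically transformed prior to being summarized". Subject-level results are listed. No change from Day 1 is planned, and no count of subjects who turn positive.

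Three other places bear on this:

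- SAP 6.3: "Immunogenicity samples with a positive titer value will undergo a log transformation for analyses", followed by "Samples with titer level less than 10 will be assigned or imputed as a log transformed titer of 1 for analyses".
- Protocol 8.9.1: "The titer of confirmed positive samples will be reported".
- Protocol 9.3.3: antibody levels are to be "summarized using descriptive statistics for the actual value at the visit".

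Neither document states the log base, or whether a sample with a titer below 10 is a negative or a low positive.

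**The concern.** Being positive after treatment is itself a response to treatment. An average restricted to positives therefore lets treatment decide who is averaged. The Day 1 mean covers only subjects who already had antibody. The Last mean covers those of them still positive plus every new positive. Prior collagenase treatment is an exclusion criterion, so the Day 1 positive group may well be small; that is an inference, since the documents give no positivity rate.

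The two means will be printed for the same table rows and will be read as a before-and-after pair. If converters have lower titers than the Day 1 positives, the difference between the means mixes a change in who is counted with a change in titer, and it can have the wrong sign.

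The percentages positive do not fill the gap. They carry no information on whether existing antibody was boosted. They identify the converters only if nobody reverts to negative.

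**Working it through.** **Inputs.** The plan gives about 32 subjects enrolled and about 24 completing. It gives no titers, positivity rates or expected values for immunogenicity, so there is no planned figure to reproduce. All titers and counts below are assumptions, on the log10 scale.

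**When the displayed mean falls.** Let m1 be the mean log titer of Day 1 positives, d their mean rise (all staying positive), f the share of Last positives that are new, and m_new the mean log titer of new positives.

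- Last mean = (1 − f)(m1 + d) + f·m_new.
- This is below m1 if and only if m_new < m1 − d(1 − f)/f.
- With m1 = 2.0 and d = 0.3, the threshold for m_new is 1.7 at f = 0.50, 1.9 at f = 0.75 and 1.97 at f = 0.90.

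**Example 1: 32 subjects.** Four Day 1 positives rise from 2.0 to 3.0; 28 negatives convert at 1.7.

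- Day 1 positives-only mean: 2.00 (n = 4).
- Last positives-only mean: (4 × 3.0 + 28 × 1.7)/32 = 59.6/32 = 1.8625 (n = 32).
- Difference: −0.1375, a ratio of 10^−0.1375 = 0.73, or a 27% fall in geometric mean titer.
- Within subjects: +1.0 in each of the 4 Day 1 positives, and 28 of 28 Day 1 negatives converted.
- Threshold from the formula: f = 28/32 = 0.875, so 2.0 − 1.0 × 0.125/0.875 = 1.86. The assumed 1.7 lies below it.

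**Same titers, fewer converters.** If 13 of the 28 convert, the Last mean is (12 + 13 × 1.7)/17 = 34.1/17 = 2.006, so there is no fall. If 14 convert, it is (12 + 14 × 1.7)/18 = 35.8/18 = 1.989, just below 2.00. With these titers the reversal therefore needs at least half of the Day 1 negatives to convert.

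**Example 2: one session group of 8.** Two Day 1 positives rise from 2.0 to 2.3; six negatives convert at 1.2.

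- Positives-only: 2.00 (n = 2) to (2 × 2.3 + 6 × 1.2)/8 = 11.8/8 = 1.475 (n = 8). The geometric mean titer goes from 100 to 29.9.
- Paired: mean change +0.30 in the two Day 1 positives; 6 of 6 Day 1 negatives treatment-induced.

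**Range.** Take 1 to 8 Day 1 positives rising from 2.0 to 2.3, with all other subjects converting. The change in the positives-only mean is:

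| Mean log titer of converters | 32 subjects | 24 subjects |
|---|---|---|
| 1.2 | −0.77 to −0.53 | −0.75 to −0.43 |
| 1.5 | −0.48 to −0.30 | −0.47 to −0.23 |
| 2.0 | +0.01 to +0.08 | +0.01 to +0.10 |

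In the last row the sign is right, but the change still understates the 0.3 rise in the Day 1 positives.

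**What the two percentages can show.** Suppose 4 of 32 are positive on Day 1 and 17 of 32 at Last. If all four stayed positive, 13 of 28 Day 1 negatives converted (46%). If all four reverted, 17 of 28 converted (61%). The planned display is identical in both cases.

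**The case against.** The strongest defence is that this is a descriptive summary in an exploratory study, with no immunogenicity hypothesis and no test of Day 1 against Last. Percent positive stands beside the mean: in Example 1 it would go from 12.5% (4/32) to 100%, and few readers would take that for a waning response. All results are listed by subject, so paired quantities can be recovered by hand. Protocol 9.3.3 also plans values at the visit, not change from baseline. And the reversal needs many converters with low titers.

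Most of this stands. It limits the point to an improvement: the paired summary would not restore something the protocol promised, and the reversal is not predicted. It does not remove the point. A listing is not a summary, and the two percentages say nothing about boosting.

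Two stronger readings are tempting, and the documents do not support either.

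- *That SAP 7.8.8 contradicts the rule for titers below 10 in SAP 6.3.* The sentence in 6.3 just before that rule concerns samples with a positive titer value, and Protocol 8.9.1 reports titers for confirmed positives. The rule can therefore be a floor for low positives at log10(10) = 1, in which case the two sections agree. What is missing is only a statement of which samples the rule covers.
- *That percent positive at Last credits pre-existing antibody to CCH.* SAP 7.8.8 presents Day 1 as well as Last, so the pre-existing rate is on display, and no text attributes all positivity at Last to treatment.

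**Conclusion.** The point holds in a limited form. As planned, the antibody-level summary compares means over groups whose membership can change with treatment, and it does not use the pre-dose sample as each subject's own baseline. Under the assumptions tried, the displayed mean moves by anything from −0.77 to +0.10 log10 while the Day 1 positives rise by 0.3 and all others convert. The wrong sign appears only when converters are numerous enough and have titers sufficiently below those of the Day 1 positives. No figure in the documents shows whether that will happen.

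The unstated log base is a small gap: a cut-off of 10 with an assigned value of 1 fits base 10, and nothing points to natural logs. The status of a titer below 10 is likewise missing detail, not an error. Overall this is a cheap improvement that would answer the stated immunogenicity objective more directly.

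**What to change.** In SAP 7.8.8, keep the percent positive and the positives-only mean. For anti-AUX-I and anti-AUX-II separately, among subjects with both a Day 1 and a post-dose sample, add:

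- the number and percent treatment-induced: Day 1 negative and post-dose positive, out of Day 1 negatives;
- the within-subject change in log10 titer among Day 1 positives, with a count of any who revert to negative.

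Show both overall as well as by number of sessions. With 3 to 6 sessions planned, 32 subjects spread evenly would give only 32/4 = 8 per group.

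As a clarification in SAP 6.3, state base 10 and say whether a titer below 10 is a negative or a low positive. Show an all-subject mean with such samples set to 1 only if the rule is meant to cover negatives.

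The cost is SAP wording and a few derived variables; no new samples are needed. The drawback is that the Day 1 positive subgroup may be very small, so its titer change should be shown with its n and read descriptively.

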## 8. CHANGE FROM PROTOCOL

This SAP is prepared based on Protocol Amendment 1: December 3, 2020. Table 20 lists any significant changes in the SAP from what is proposed in the protocol.

**Table 20: Changes from Protocol**

Text in Protocol	Change in SAP	Justification
N/A		

## 9. REVISION HISTORY

Non-editorial changes made to any of the modules of this SAP will be recorded in Table 21.

**Table 21: Revision History**

Version	Date	Revision Author	Comments
1.0	09-Nov-2020	[REDACTED]	Original
1.1	24-Jun-2021	[REDACTED]	SAP updated as per Protocol Amendment 1

